- Collection of results of syphilis and HIV testing (performed according to routine practice)
- Sample collection:
 - o Urine sample (first-void) (Ng/Ct NAAT)
 - o Pharyngeal swab (Ng/Ct NAAT)
 - o Anorectal swab (Ng/Ct NAAT)

Visit month 12 (can be between one week early and 6 weeks late):

- Ask if symptoms compatible with STI
- Physical examination if symptomatic
- STIs diagnosed since last visit (at study site or outside)
- Antibiotic usage
- Collection of results of syphilis and HIV testing (performed according to routine practice)
- Sample collection:
 - o Urine sample (first-void) (Ng/Ct NAAT)
 - o Pharyngeal swab (Ng/Ct NAAT)
 - o Anorectal swab (Ng/Ct NAAT)
- Question regarding sexual behaviour
- PrEP questionnaire (only at ITM)
- Experience of study participation and preference for screening vs. no screening of Ng/Ct (only at ITM)

Unscheduled visits:

- Visits for treatment of detected STIs:

If any asymptomatic (in screening arm) or symptomatic (in both arms) STI is diagnosed via screening (including Ct, Ng, syphilis, HIV or hepatitis C) at any stage during the study, the current practice of contacting the PrEP recipient (typically by telephone) as soon as the test result is known (typically within 7 days) will be followed. The person will be asked to return to the clinic at their earliest convenience for standard management, including contact tracing. If the week-prior testing schema is used then the participant will be typically treated on the day of the clinic visit. These STIs will be treated according to our current guidelines [3]. Participants in the non-screening arm who come for STI testing at unscheduled study visits for example if they have symptoms of an STI, will be informed of the STI diagnosis according to local best practice guidelines.

Persons with an HIV diagnosis will be offered optimal antiretroviral therapy and further best practice management according to our existing PrEP protocol [5]. They will exit this study after the diagnosis of HIV is made.

As is currently the case for all PrEP recipients, participants of this study will be able to attend the PrEP/STI clinic at any point in between the scheduled visits for any health including mental-health related concerns. Participants will be encouraged to attend the clinic for any symptoms compatible with an STI.

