Any STIs (Ng, Ct, syphilis, HIV) diagnosed at non-scheduled visits between 0 and 12 months will be included in the primary and secondary outcome. Every effort will be made to obtain laboratory confirmation of these infections and only laboratory confirmed cases will be included in the study outcomes.

Visits as a result of partner notification:

Participants in the non-screening arm will also be tested and eventually treated empirically for Ng/Ct and other STIs if they are alerted for this purpose by partner notification. These visits will be classified as unscheduled visits and they will be tested for Ng/Ct at all three sites. They will also be encouraged to receive empiric therapy for Ng, CT or both according to which STI they were in contact with and what the nature of this contact was in accordance with IUSTI guidelines (<https://www.iusti.org/regions/europe/euroguidelines.htm>).

Visits to assess test-of-cure:

The Belgian National PrEP guidelines do not make a recommendation as to whether or not a test-of-cure is required following treatment for Ng or Ct. In practice most centres reserve performing a test of cure for gonorrhoea infections with a high risk of antimicrobial resistance (such as those from individuals epidemiologically linked to resistant infections) as well as infections with a documented elevated or borderline gonococcal MIC for ceftriaxone. In large part this limitation on performing routine tests of cure is related to patient preference. PrEP patients are followed up 3 monthly which is onerous on patients. They then need to come back for therapy every time they are diagnosed with Ng/Ct. If they need to add an extra test of cure visit to this schedule then many patients regard this as unacceptable or simply not achievable. We will continue with this approach and document all test of cure visits as unscheduled visits. When done, test of cure visits will be performed at the earliest 14 days after the receipt of effective Ng/Ct therapy to rule out

persisting dead DNA causing false positive NAAT test results. Because any positive Ng/Ct test from the test of cure visits is considered a non-resolved old infection, these will not be included in the primary or secondary outcomes as new infections. If however the test of cure was to assess if an Ng infection had cleared and a new Ct infection was detected at the test of cure visit then this would be included as a new infection in the primary and secondary study outcomes.

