If a patient has evidence of clinical treatment failure this is a separate issue and we instruct patients to return for further tests if they have persistence of their symptoms. This is also not considered a new infection and will thus not be included in the primary or secondary outcomes as new infections.

All the following investigations are optional for any unscheduled visit:

- Ask if symptoms compatible with STI
- Physical examination
- STIs diagnosed since last visit (at study site or outside)
- Antibiotic usage
- Collection of results of syphilis and HIV testing (performed according to routine practice)
- Sample collection:
 - o Urine sample (first-void) (Ng/Ct NAAT)
 - o Pharyngeal swab (Ng/Ct NAAT)
 - o Anorectal swab (Ng/Ct NAAT)
 - o Pharyngeal or anorectal swab for every site that was Ng NAAT positive (Ng culture)

As is the case for routine PrEP visits currently, at every visit (scheduled or unscheduled) there will be some time for STI counselling and discussions of any concerns of the participants related to the study or not.

Assessing and confirming if a study participant has had a Ct/Ng infection in between study visits.

At the month 3, 6, 9 and 12 visits, the participants will be asked if they have had any symptoms of an STI since their last visit or if they have been tested for an STI since their last visit. If the answer to either of these questions is 'yes', then the study team will proceed with the Ng/Ct diagnosis verification protocol.

1. Obtain further information as to what the symptoms were, if any, and what anatomical sites were tested
2. Find out at which health provider (e.g. general practitioner (GP)) was the diagnosis made
3. Establish what antimicrobial therapy was received
4. Laboratory confirmation will be obtained of test results. The following will be regarded as laboratory proof of a Ct/Ng diagnosis:
 - a. The participant has documented proof of a diagnosis of Ng/Ct based on a laboratory report.
 - b. Laboratory evidence of a positive Ng/Ct diagnosis based on NAAT or Ng culture that can be obtained by the study team via: (1) online laboratory reporting systems

such as COZO, (2) telephonic contact with the laboratory or (3) telephonic contact with the health provider who performed the test.

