Over 4 FU visits, this yields an average of 0.72 diagnoses per subject. Using a Poisson regression model with $\log(\text{number of visits})$ as offset, the 95% confidence interval of the log ratio (no screening vs. screening) is calculated. The 'no screening' arm is considered to be non-inferior if there is an increase of maximal 25% in number of diagnoses (i.e. increase of an average of 0.72 to 0.90 per 4 visits). The 'no screening' arm is proven to be non-inferior if the upper limit of the 95% confidence interval is lower than $\log(1.25)$. The required sample size to detect non-inferiority of the 'no screening' arm is calculated by simulation, assuming no difference between arms.

Assuming that 95% of the participants will have data on all 4 visits, and 5% will have data on only 3 visits, the required sample size to obtain 80% power is 912. Assuming an additional 10% drop out rate we will need to enroll 1014 participants.

The current number of PrEP participants at the ITM/HSP/EH/CHU/UZG is 803/739/290/260/240, respectively. At all 5 centres this number is increasing by approximately 20% per year. 99.7% of these individuals are MSM and over the age of 18. We estimate that 80% of the 2332 PrEP participants in these five centres will agree to participate. This number (n=1866) exceeds the number we need to enroll in the study (n=1014). By the commencement of the study (begin 2020) we estimate we will have 1518/886/464/314/298 individuals in the PrEP cohorts at the ITM/HSP/EH/CHU/UZG whom we will be able to screen for participation.

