11.3.2 Primary outcome analysis

We will analyse the primary outcome both using Intention-to-Treat and Per-Protocol approaches, with Per-Protocol as primary approach. In the Intention-to-Treat analysis, all participants will be analysed according to their randomized allocation, even in case they receive another intervention, show protocol violations prior to or during the study, or are lost-to follow. In the per-protocol analysis only participants who receive intervention as planned, and follow the protocol as planned

are included. If the person urgently requires knowing if they are infected with Ng/Ct or not this will be done by repeat testing for these infections. If this test is positive for Ng/Ct then this will be counted as an intervisit infection in the final analysis. In each arm, the incidence of Ng plus Ct will be estimated together with 95% confidence interval. Estimates will be based on a Poisson regression model with number of diagnoses as dependent variable, arm as independent variable, log(number of visits) as offset and a random intercept for site. This model will also provide an estimate of the log incidence rate ratio (no screening versus screening), together with 95% confidence interval. The 'no screening' arm is proven to be non-inferior if the upper limit of the 95% confidence interval is lower than log(1.25).

Visits with missing data on the diagnosis of Ng or Ct, will be excluded from the calculation of the incidence rate (excluded both from numerator and denominator).

Subgroup analysis:

We will conduct a prespecified sensitivity analysis to assess the incidence of Ng plus Ct in screening vs. non-screening arms ***in participants with lower-risk behavior***. An individual with lower-risk behavior is defined a priori as those individuals who report 4 or fewer partners per 3-month period in all 5 relevant 3 month periods. These periods are the 3-months prior to study enrollment as well as the four 3 month periods during study follow up). The analysis will be analogous to the analysis of the primary objective, but restricted to participants with lower-risk behavior.

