11.4 Data collection for economic evaluation

One of the goals of the KCE Trials programme is to improve the efficiency of the healthcare system. This protocol has been designed with a later possible economic analysis in mind. The planned economic analysis is briefly described below, together with the variables collected in this protocol for this purpose. For the sake of clarity, the economic analysis is not a part of this trial. The decision to conduct such economic analysis will depend on the effectiveness results of this trial.

The major expected costs and benefits of 3x3 screening in MSM are detailed in Table 3. Given the available evidence, and in particular the lack of any RCTs assessing the effectiveness of screening, we are unable to a priori know if screening does result in the first two benefits listed in the table – reduction of spread of Ng/Ct and fewer episodes of symptomatic disease. As outlined in the ‘Background’ section, screening may result in arrested immunity and thereby paradoxically increase the incidence of symptomatic infections and the spread of Ng/Ct. The current RCT and its envisioned second phase, will thus provide useful empirical estimates of what these effect sizes and directions are. The direct costs of screening include the cost of testing, consultation fees for the initial visit, the visit to receive treatment (for those testing positive) and in the case of a positive Ng molecular test perform culture and sensitivity, the follow up visit 2 weeks later to assess treatment response (for Ng infections), the price of antimicrobial therapy – including cost of administering injections (for Ng). The indirect costs of screening include the time taken to attend consultations and the adverse effects of the high levels of antimicrobials on the individual’s health, including their microbiome/resistomes and the selection for antimicrobial resistance in Ng/Ct, other STIs and other bacteria in their microbiomes. This adverse effect will operate at both an individual and population level.

The important link between perception of Ng/Ct screening efficacy and impact on QoL

Screening in and of itself would not be predicted to have a direct effect on a PrEP participant’s quality of life. If, however, a participant knew or thought that screening reduced his risk of symptomatic Ng/Ct or of Ng/Ct transmission to his partners then participating in screening could improve his quality of life via the following two plausible cognitions:

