5.2. Efficacy study endpoints

Primary endpoint

Incidence of Ng plus Ct detected at any site.

Numerators: Cumulative number of laboratory-confirmed diagnoses of Ng plus Ct in 12 months in screening/non-screening arms. Each participant can only contribute one diagnosis of Ct and one diagnosis of Ng per (scheduled or unscheduled) visit - regardless of number of sites infected. Thus each participant can contribute up to 2 diagnoses (Ct/Ng) at each (scheduled or unscheduled) visit. The numerator includes laboratory-confirmed diagnoses made between scheduled visits, performed inside or outside of the study.

Denominators: Number of scheduled study visits with available results for the diagnosis of Ng/Ct. The denominator does not include unscheduled visits.

The diagnosis of Ng and Ct will be made via nucleic acid amplification testing (NAAT) performed on rectal and pharyngeal swabs and urine.

If the person urgently requires knowing if they are infected with Ng/Ct or not this will be done by repeat testing for these infections. If this test is positive for Ng/Ct then this will be counted as an intervisit infection in the final analysis.

In the primary analysis, the primary endpoint (as described above) includes all Ng/Ct diagnoses. Hence it is implicitly assumed that every diagnosis is a new infection. It is however possible that an Ng/Ct infection detected at the 3 to 12 month visit in the non-screening arm is simply a non-resolved infection from the prior visit. This could spuriously increase the measured incidence in the non-screening group. Because this risk only applies to the non-screening arm it results in a bias towards exaggerating the effect of screening on incidence. As such if our study finds that non-screening is non-inferior to screening this finding could not be explained by this bias. In a sensitivity analysis, the numerator of the primary endpoint will only include diagnoses if there was a negative test result at the prior visit.

Because any positive Ng/Ct test from the test of cure visits is considered a non-resolved old infection, these will not be included in the primary or secondary outcomes as new infections. If however the test of cure was to assess if an Ng infection had cleared and a new Ct infection was detected at the test of cure visit then this would be included as a new infection in the primary and secondary study outcomes.

Secondary endpoints

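### As written, the primary numerator can count one infection twice when a recall-for-treatment visit re-tests positive; such duplicates fall mainly in the screening arm and push the ratio towards non-inferiority

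*Protocol*

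**What the plan says.** Counting unit. Protocol 4.3.1 and 11.1 and SAP 5.2 define the numerator per visit, not per infection episode: "Thus each participant can contribute up to 2 diagnoses (Ct/Ng) at each (scheduled or unscheduled) visit". Protocol 4.3.1 and SAP 5.2 also state that the primary analysis treats every diagnosis as a new infection. Protocol 8.7 confirms that unscheduled visits feed the endpoint: "Any STIs (Ng, Ct, syphilis, HIV) diagnosed at non-scheduled visits between 0 and 12 months will be included in the primary and secondary outcome", provided the infection is laboratory confirmed. The denominator is scheduled visits only.

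Exclusions. There are two. A positive for the original organism at a test-of-cure visit, at the earliest 14 days after therapy, is treated as an old infection (Protocol 8.7, SAP 5.2). Clinical treatment failure is also not counted (Protocol 8.7); the SAP does not repeat this.

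Recall visits. The first type of unscheduled visit in Protocol 8.7 is the visit to treat a detected STI. After a positive result, "The person will be asked to return to the clinic at their earliest convenience for standard management, including contact tracing". For asymptomatic infections this applies to the screening arm; for symptomatic infections, to both arms. The no-screening arm is told only its month 0 and month 12 results.

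Sampling at unscheduled visits. The optional list in Protocol 8.7 contains three-site NAAT and also "Pharyngeal or anorectal swab for every site that was Ng NAAT positive (Ng culture". Protocol 11.4, on the costs of screening, mentions the visit to receive treatment and "in the case of a positive Ng molecular test perform culture and sensitivity".

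**The concern.** A recall visit takes place before therapy, so neither exclusion covers it. The protocol foresees that a site already known to be NAAT positive may be swabbed again, and it permits a repeat NAAT. If that sample is positive and the rule is applied literally, the month 3 infection is counted once at month 3 and again at the recall visit, with no extra denominator.

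This matters because the opportunity differs by arm. The Background section describes the vast majority of these infections as asymptomatic, and asymptomatic positives at months 3, 6 and 9 lead to recall only under screening. Duplicates therefore raise mainly the comparator rate, which makes non-inferiority easier to declare. The plan discusses a distortion in the opposite direction (unresolved infections in the no-screening arm) but not this one.

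A related gap concerns month 0. Recall for a month 0 positive occurs in either arm and falls inside the 0 to 12 month window, so a positive re-test there would enter a baseline infection as a follow-up diagnosis.

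**Working it through.** **1. Reproduce the plan's figure.** Inputs from Protocol 11.1: a margin defined as an "increase of maximal 25% in number of diagnoses", 1:1 allocation (8.3), a two-sided 95% interval, and the statement that "the required sample size to obtain 80% power is 912".
- Rate per visit: 0.79 × 0.15 + 0.18 × 0.28 + 0.03 × 0.34 = 0.1791. Over 4 visits: 0.716, which the plan gives as 0.72.
- Mean visits: 0.95 × 4 + 0.05 × 3 = 3.95, so 0.1791 × 3.95 = 0.7074 diagnoses per participant.
- Events needed: 4 × (1.96 + 0.8416)² / (ln 1.25)² = 631.
- N = 631 / 0.7074 = 892, which is 2.2% below 912. Simulating the plan's own visit table at 456 per arm gave 80.4% power (site effect left out). Enrolment: 912 / 0.90 = 1013.3, rounded up to 1014. The plan's figures are reproduced.

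**2. Inputs for the double count.**
- From the documents: 0.72 diagnoses per screening participant, and a true ratio at the margin, so 0.90 without screening.
- Assumption: half of diagnoses are Ng. The Background gives a prevalence of about 10% for each organism.
- Assumption: recalls after months 3, 6 and 9 count (three of four visits). Recall after month 12 is left out.
- Assumption: 10% of no-screening infections are recalled because they are symptomatic.
- Assumption, not in the documents: q, the share of Ng recalls that yield a second recorded positive.

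**3. Formulae.**
- Ng recalls per screening participant: 0.72 × 0.5 × 0.75 = 0.27.
- Screening mean: 0.72 + 0.27q. No-screening mean: 0.90 + 0.27 × 1.25 × 0.10 × q.
- Standard error implied by 80% power: ln 1.25 / (1.96 + 0.8416) = 0.0796.
- Chance of declaring non-inferiority: Φ[(ln 1.25 − ln observed ratio) / 0.0796 − 1.96].

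**4. Results at a true ratio of 1.25.**

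| q | Screening mean | No-screening mean | Observed ratio | False non-inferiority |
|---|---|---|---|---|
| 0 | 0.720 | 0.900 | 1.25 | 2.5% |
| 5% | 0.734 | 0.902 | 1.23 | 4.0% |
| 10% | 0.747 | 0.903 | 1.21 | 6.1% |
| 25% | 0.788 | 0.908 | 1.15 | 17% |

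**5. Centres without a separate recall visit.** Where samples are taken the week before, treatment is typically given at the clinic visit itself. Protocol 8.7 names HSP as one such centre. If HSP recruits in proportion to cohort size (739 of 2332, 32%; Protocol 11.1) and has no recall visits, 0.27 becomes 0.27 × (1 − 739/2332) = 0.184. False non-inferiority is then 4.7% at q = 10% and 10% at q = 25%.

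**6. Cross-check under a different assumption.** A simulation of the plan's visit table (2,500 runs per setting) duplicated a share r of all screening-arm diagnoses at months 3, 6 and 9, Ng and Ct alike, and none in the no-screening arm. False non-inferiority (Poisson interval) was 8% at r = 5% and 19% at r = 10%, against 2.8% with no duplicates. These figures answer a wider question than the table and do not validate q. They show that the direction is robust and that small shares matter. Letting month 0 recalls count in both arms at the same share barely changed the result (21% at r = 10%).

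**The case against.** The recall re-test is inferred. Protocol 8.7 describes recall as management of an infection already found and does not require a repeat test there; the sampling list is an optional menu for every kind of unscheduled visit. Where testing is intended, as after partner notification, the protocol says so. One can also argue that an infection already reported is not diagnosed at the recall visit. This limits the size but does not supply a rule: the numerator is defined per visit, and the authors thought an explicit exclusion necessary for the comparable re-test after treatment.

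Culture may not count. Protocol 4.3.1 and SAP 5.2 name NAAT as the diagnostic method, and Protocol 11.4 describes an economic analysis outside the trial. Yet Protocol 8.7 accepts Ng culture as laboratory proof for infections between visits. The text leaves this open; if culture does not count, only repeat NAATs contribute and q is lower.

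A reader might infer that duplicates arise almost solely under screening. The documents do not support that. Symptomatic and month 0 recalls occur in both arms, and an untreated no-screening infection can itself be counted again at a partner-notification visit, an urgent repeat test or the next scheduled visit. Mainly is the defensible word.

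A reader might also infer that the plan claims all misclassification works against non-inferiority. It does not: Protocol 4.3.1 and SAP 5.2 make that claim only for unresolved infections.

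Finally, the sensitivity analysis requiring a negative test at the prior visit would remove the duplicates if the prior visit is the one that triggered recall. That term is undefined, the analysis also drops genuine reinfections, and it does not decide the primary claim.

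**Conclusion.** The gap is real and its direction is clear: followed literally, the counting rule lets a positive recall re-test enter the primary numerator twice, mainly in the screening arm, and this lowers the ratio. The size cannot be established. Under the Ng-only assumptions above, re-test positivity of 10% or 25% at recall takes false non-inferiority from 2.5% to about 6% or 17%, or about 5% or 10% if HSP has no recall visits. All of these rest on q, which the documents do not give.

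A reader might go further and conclude that the primary comparison as a whole is biased towards non-inferiority. The documents do not support that either: persistent infection in the no-screening arm pushes the ratio up, and the net of the two effects is unknown. The point is therefore a should-fix rather than a must-fix: an undefined case in the primary endpoint that is cheap to close.

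**What to change.** In SAP 5.2 and Protocol 4.3.1 and 11.1, add a rule with three parts:
- At an unscheduled visit made to treat a positive result already reported to the clinic, in either arm and including a month 0 result, a positive for the same organism is part of the triggering diagnosis and is not counted again.
- A different organism found at that visit still counts as new.
- The rule does not apply to unreported, untreated positives in the no-screening arm. Later diagnoses there through symptoms, partner notification or an urgent test count as they do now.

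The third part is essential. A broader rule that merged every same-organism positive between a positive sample and its treatment would leave the window open for months in the no-screening arm, where month 3, 6 and 9 positives go untreated. It would delete genuine later infections and itself favour non-inferiority.

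Also state whether an Ng culture taken within the study counts as a diagnosis, and repeat the treatment-failure exclusion in the SAP.

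Cost: a few sentences and one derivation step using organism, visit type and dates. The sample size stays at 912 evaluable and 1014 enrolled, because the planning model uses scheduled visits only. The downside is that a true same-organism reinfection between the sample and the recall visit, typically about a week, would not be counted.
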